### 2 Protocol Summary

Study Compound: Atogepant

Phase: 3

#### Study Objective:

To evaluate the safety and tolerability of treatment with atogepant 60 mg daily (QD) for the prevention of migraine in participants with episodic migraine (EM) over 52-week duration.

#### Clinical Hypotheses:

Atogepant 60 mg QD is safe and well tolerated when administered over 52 weeks for the prevention of migraine in participants with EM.

#### Study Design

Structure: Multicenter, randomized, open-label, 52-week long-term safety study conducted in the United States.

Duration: The study will consist of a 4-week screening and baseline period, a 52-week treatment period, and a safety follow-up period of an additional 4 weeks, for a total duration of 60 weeks.

Study Intervention: Atogepant 60 mg QD

Control: Oral standard of care (SOC) migraine prevention medication

Dosage/Dose Regimen: Atogepant 60 mg QD will be administered for 52 weeks.

Participants randomized to oral SOC migraine prevention medication will be treated with a medication recognized as safe and effective for the prevention of migraine (Evers 2009, Hoffmann 2014, Schürks 2008, Silberstein 2012, Steiner 2007). The selection of this initial migraine preventive medication will be based on investigator judgment in consultation with the participant.

Randomization: Participants will be randomized (5:2) to the following treatment groups: Atogepant 60 mg QD or oral SOC migraine prevention medication.

A minimum of 200 participants randomized to atogepant must be classified as *De Novo* Participants (see definition below under Study Population Characteristics).

Visit Schedule: After the screening and randomization visits, study visits will occur every 4 weeks for the duration of the 52-week study. For participants randomized to the atogepant arm, a safety follow-up visit will occur 4 weeks after the last dose of atogepant. For participants randomized to oral SOC migraine prevention medication a safety follow-up visit will occur 4 weeks after the last visit in the treatment period. There will be 16 scheduled clinic visits. For details, please see Table 1, the Schedule of Visits and Procedures.

This study will consist of 2 groups of participants: De Novo Participants and Study CGP-MD-01 Completers (see definition below under Study Population Characteristics).

De Novo Participants and Study CGP-MD-01 Completers will complete all 16 study visits, including the 28-day screening period.

#### Study Population Characteristics

Number of Participants/Sites: Approximately 700 participants will be randomized (500 participants in the atogepant arm and 200 participants in the oral SOC migraine prevention medication arm) from approximately 115 centers in the United States. Two groups of participants will be eligible to participate in this study.

- De Novo Participants Participants who did not participate in any previous study with atogepant who meet the
  inclusion criteria and do not meet the exclusion criteria may be enrolled in this study (referred to as De Novo
  Participants).
- Study CGP-MD-01 Completers Participants who completed Study CGP-MD-01 (Visit 8) without significant
  protocol deviations (eg, noncompliance to protocol-required procedures) and who meet the inclusion criteria
  and do not meet the exclusion criteria (referred to as CGP-MD-01 Completers).
  - For participants who completed Study CGP-MD-01, there will be a time gap from the time of completion
    of Study CGP-MD-01 to the start of this study. For this reason, participants from Study CGP-MD-01 will
    need to re-establish study eligibilty. In addition, these participants will have their baseline migraine days
    re-established during the screening period but this will not be used as an inclusion/exclusion criteria for
    randomization.
- Condition/Disease: Migraine with aura or migraine without aura (ICHD-3 Section 1.1 or Section 1.2; see Section 12.1.1)

#### Key Inclusion Criteria:

#### All participants:

Participant is a candidate to be prescribed at least one of the protocol-defined acceptable oral SOC migraine
prevention medications, and the participant is willing to accept SOC treatment.

#### For De Novo Participants only:

- Male or female participants age 18 to 80 years, inclusive, at Visit 1
- At least a 1-year history of migraine with or without aura consistent with a diagnosis according to the International Classification of Headache Disorders, 3rd Edition (ICHD-3 2018)
- Age of the participant at the time of migraine onset < 50 years

- History of 4 to 14 migraine days per month (see Section 6.1.1 for definition) in the 3 months prior to Visit 1 in the investigator's judgment

#### For CGP-MD-01 Completers only:

 Eligible participants who completed Study CGP-MD-01 (Visit 8) without significant protocol deviations (eg, noncompliance with protocol-required procedures) and who did not experience an AE that, in the investigator's opinion, may indicate an unacceptable safety risk

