# 4.2 Study Population Characteristics

There will be 2 groups of participants eligible to participate in this study.

- De Novo Participants: participants with no previous exposure to atogepant and who
  meet the inclusion criteria and do not meet the exclusion criteria (referred to as
  De Novo Participants)
- Study CGP-MD-01 Completers: participants who completed Study CGP-MD-01 (Visit 8) without significant protocol deviations (eg, noncompliance to

protocol-required procedures) and who meet the inclusion criteria and do not meet the exclusion criteria (referred to as CGP-MD-01 Completers)

o For participants who completed Study CGP-MD-01, there will be a time gap from the time of completion of Study CGP-MD-01 to the start of this study. For this reason, participants from Study CGP-MD-01 will need need to re-establish study eligibilty. In addition, these participants will have their baseline migraine days re-established during the screening period but this will not be used as an inclusion/exclusion criteria for randomization.

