#### 5.4 Treatment Allocation Ratio

Participants will be randomized to the following 2 arms in a 5:2 ratio:

- Atogepant 60 mg QD (n = 500)
  - Note: A minimum of 200 participants randomized to atogepant must be classified as De Novo Participants
- Oral SOC migraine prevention medication (n = 200)

[figure not shown]
No stratification will be performed.

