## 7.5 Sample Size Calculation

This study plans to randomize a total of 700 participants. Participants will be randomized 5:2 to receive atogepant 60 mg QD or oral SOC migraine prevention medication. Based on data from previous studies (Aurora 2011; Rapoport 2006), it is estimated that approximately 60% of those participants will complete 6 months of treatment, and of those, 65% will complete 12 months of treatment.

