The Safety Population includes all participants who received at least 1 dose of study intervention (atogepant or SOC medication). All safety analyses will be performed using the Safety Population, which is defined for the atogepant arm, as well as the SOC arm, and based on the treatment actually received, regardless of assigned treatment according to the planned randomization. Participants will be summarized according to the study treatment received for majority of treatment period.

7 Participant Disposition

The number of participants in the ITT and Safety Populations will be summarized by treatment group; the number of participants in the mITT Population will be summarized for the atogepant arm; the number of participants screened will be summarized overall. The number of participants in the ITT Population will also be summarized by treatment group for each enrollment category (De Novo Participants and CGP-MD-01 Completers). For CGP-MD-01 Completers, the number of participants in the placebo arm and pooled atogepant arm will be further summarized. In addition, the number of participants in the Safety Population will be summarized by treatment group

Screen-failure participants (ie, participants screened but not randomized) and the associated reasons for failure to randomize will be tabulated overall for the all screened participants. The number and percentage of participants who enter the open-label treatment period, complete the open-label treatment period and of participants who prematurely discontinue during the same period will be presented for each treatment group and pooled across treatment groups for all randomized participants. The reasons for premature discontinuation from the open-label treatment period as recorded on the termination pages of the electronic case report forms will be summarized (number and percentage) by treatment group. The percentage is relevant to the total number of randomized participants. Similar disposition information will be presented for the safety follow-up period. All randomized participants who prematurely discontinue during the open-label treatment period or the safety follow-up period will be listed by discontinuation reason.

8 Demographic and Other Baseline Characteristics

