11.1 Adverse Events

Adverse events will be coded by system organ class and preferred term using the Medical Dictionary for Regulatory Activities (MedDRA), version 21.0 or newer.

An AE will be considered as a treatment-emergent adverse event (TEAE) if the AE began or worsened (increased in severity or became serious) on or after the date of the first dose of open-label study treatment. For participants randomized to the atogepant arm, an AE that occurs more than 30 days after the last dose of open-label study treatment or Visit 16 whichever comes later will not be counted as a TEAE. For participants randomized to the SOC arm, an AE that occurs after Visit 16 will not be counted as a TEAE. Per case report form instructions, a new AE record will be created for any AE that worsens; therefore, for participants randomized to the atogepant arm, TEAEs can be identified as those AEs with recorded onset date on or after the date of the first dose of open-label study treatment within 30 days after the last dose of open-label study treatment or Visit 16 whichever comes later. For participants randomized to the SOC arm with available Visit 16 information, TEAEs can be identified as those AEs with recorded onset date on or after the date of the first dose of open-label study treatment and up to Visit 16; for participants randomized to the SOC arm but missing Visit 16 information, TEAEs are identified as those AEs with recorded onset date on or after the date of the first dose of open-label study treatment. An AE will be considered as a treatment-emergent SAE (TESAE) if it is a TEAE that also meets SAE criteria. TEAEs that started after the date of last dose of study treatment will be considered as newly emergent.

Overall summary of AEs will be provided on a per-participant basis for categories of TEAEs, treatment-related TEAEs, deaths, TESAEs, and TEAEs leading to study discontinuation.

The number and percentage of participants reporting TEAEs in each treatment group will be tabulated by system organ class and preferred term, and further categorized by severity to the study treatment.

The number and percentage of participants reporting treatment-related TEAEs in each treatment group will be tabulated by system organ class and preferred term.

The number and percentage of participants reporting newly emergent TEAEs in the atogepant arm will be tabulated by system organ class and preferred term.

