APPENDIX I. REPORTING SELECTED LABORATORY PARAMETERS IN CONVENTIONAL UNIT

All clinical laboratory parameters will be reported in the International System (SI) units as standard practice. In addition, descriptive statistics for values and changes from baseline in conventional units at all assessed visits will be reported for selected laboratory parameters as listed in Table 21-1 below.

Table 21-1 List of Selected Parameters to be Reported in Conventional Units

Number	Laboratory Parameter	Conventional Unit	Decimal Places
1	Alanine Aminotransferase (SGPT)	U/L	0
2	Albumin	g/dL	1
3	Alkaline Phosphatase	U/L	0
4	Aspartate Aminotransferase (SGOT)	U/L	0
5	Bilirubin, Direct (Conjugated)	mg/dL	1
6	Bilirubin, Indirect (Unconjugated)	mg/dL	1
7	Bilirubin, Total	mg/dL	1
8	Blood Urea Nitrogen	mg/dL	0
9	Calcium	mg/dL	1
10	Cholesterol, HDL	mg/dL	0
11	Cholesterol, LDL	mg/dL	0
12	Cholesterol, LDL direct and calculated (combined) (This lab parameter could be the same as #11)	mg/dL	0
13	Cholesterol, Total	mg/dL	0
14	Creatine Kinase	U/L	0
15	Creatinine	mg/dL	1
16	Glucose	mg/dL	0
17	Insulin	uIU/mL	1
18	Triglycerides	mg/dL	0
19	Uric Acid	mg/dL	1
20	Hemoglobin	g/dL	1

Patient narratives will also include the values in conventional units for the selected lab parameters (Table 21-1). That will be accomplished by presenting the values in conventional units within the parentheses next to the values in SI units. As shown in Table 21-2 below for 'Bilirubin, Total' parameter, for which 'umol/L' is the SI unit and 'mg/dL' is the conventional unit.

Table 21-2 Presenting Laboratory Data Using SI and Conventional Units in Narratives

LABORATORY DATA						
Lab Test	Normal Range VISIT01 VISIT05 VIS					VISIT07
		Low	High	2012-07-03	2012-08-07	2012-09-04
CHEMISTRY	Bilirubin, Total (umol/L(mg/dL))	0 (0)	18.81 (1.1)	6.84 (0.4)	5.13 (0.3)	5.13 (0.3)

APPENDIX II. SUMMARY OF CHANGES FOR AMENDMENT 1

Amendment #1 specifies the following changes to the Statistical Analysis Plan for Study 3101-302-002 dated 18 Mar 2019.

- 1. For safety analyses, participants will be summarized according to the study treatment period received for majority of treatment period.
- 2. Remove ISS related subgroup analyses in the summary tables for disposition, exposure, and TEAEs.
- 3. Update the age groups for demographic parameters.
- 6. Concomitant medication use will be summarized for open-label treatment period and safety follow-up period.
- 7. Update treatment duration in align with ISS.

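### The visible AE tables pool De Novo participants with CGP-MD-01 Completers, some of them already selected for tolerating atogepant, so atogepant AE and AE-discontinuation rates may understate those for new users

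*Protocol*

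**What the plan says.** **Who enters.** Two groups are eligible: De Novo participants and CGP-MD-01 Completers. Under the key inclusion criteria in the Protocol Summary, Completers must have finished the earlier study without significant protocol deviations and be people "who did not experience an AE that, in the investigator's opinion, may indicate an unacceptable safety risk". De Novo participants have no equivalent criterion.

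**How many.** Protocol 4.1 and 5.4 plan 500 participants on atogepant and 200 on SOC. At least 200 of those on atogepant must be De Novo. Protocol 5.4 adds: "No stratification will be performed".

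**What is tabulated.** SAP 11.1 states: "The number and percentage of participants reporting TEAEs in each treatment group will be tabulated by system organ class and preferred term". Treatment-related TEAEs, TESAEs, common TEAEs and TEAEs leading to discontinuation are also given by treatment group. Newly emergent TEAEs are given for the atogepant arm only. None of the visible AE tables is split by enrolment category.

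**What is already held.** SAP Section 7 (Participant Disposition) counts the ITT Population by treatment group within enrolment category, and goes further: "For CGP-MD-01 Completers, the number of participants in the placebo arm and pooled atogepant arm will be further summarized".

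**Who is De Novo.** The Protocol Summary defines the group as "Participants who did not participate in any previous study with atogepant". Protocol 4.2 uses "participants with no previous exposure to atogepant", and SAP Section 4 uses the same exposure-based wording.

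**The concern.** Safety and tolerability of atogepant over 52 weeks is the study's only stated objective, and Protocol 3.1 says that the SOC arm is there to provide comparative safety data. The figures most readers will take away are the percentages of atogepant participants with AEs and with AEs leading to discontinuation. They will read them as what a patient starting the drug can expect.

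A Completer who took atogepant in CGP-MD-01 is not such a patient. That person has taken the drug to the end of a study without an AE that the investigator judged an unacceptable risk. People who stopped early because of an AE cannot be in this group. If enough of the arm is of this kind, and if early tolerance predicts later tolerance, the pooled rate lies below the rate for new users. The same people were not selected for having tolerated any SOC drug, so the mix has been screened on experience with one arm's drug only. Pooled tables give the reader no means of checking any of this.

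The two De Novo definitions raise a smaller problem of the same kind. A Completer who received placebo has taken part in an atogepant study but has not been exposed to atogepant. On wording alone, that person fails the first definition and meets the second, so could fit both groups and count towards the floor of 200.

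**Working it through.** **The plan's own figures.** Protocol 7.5: "This study plans to randomize a total of 700 participants". At 5:2 this gives 700 × 5/7 = 500 on atogepant and 700 × 2/7 = 200 on SOC, as stated. The visible text gives no event rate, effect size or power for safety, so there is no safety calculation to reproduce.

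**Largest Completer share.** 500 − 200 = 300, and 300/500 = 60%. This is a ceiling implied by the floor. No planned number of Completers is visible.

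**Model.** Let
- p = the De Novo rate on atogepant;
- w = the Completer share of the atogepant arm (0 to 0.60);
- f = the share of those Completers previously on atogepant (not in the documents);
- RR = the risk in previously exposed Completers relative to De Novo (not in the documents).

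Prior-placebo Completers are given the De Novo rate. Then

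pooled rate = (1 − w)p + w(1 − f)p + w·f·RR·p,

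so pooled / De Novo = 1 − w·f·(1 − RR).

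| w | f | RR = 0.5 | RR = 0.7 | RR = 1 |
|---|---|---|---|---|
| 0.6 | 1 | 0.70 | 0.82 | 1.00 |
| 0.6 | 0.5 | 0.85 | 0.91 | 1.00 |
| 0.3 | 1 | 0.85 | 0.91 | 1.00 |
| any | 0 | 1.00 | 1.00 | 1.00 |

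For example, 1 − 0.6 × 1 × 0.5 = 0.70 and 1 − 0.6 × 0.5 × 0.3 = 0.91.

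**On an absolute scale.** With an assumed De Novo AE-discontinuation rate of 10%, the pooled rate is 7.0% to 8.2% in the first row and 8.5% to 9.1% in the second and third. If the SOC rate is the same in both enrolment categories (a further assumption), the arm difference for the enrolled mix differs from that for new users by the same amount, at most 10.0 − 7.0 = 3.0 points in this table.

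**Effect of unstratified randomisation.** At a Completer share of 60%, the chance difference between arms has SE = √(0.6 × 0.4 × (1/500 + 1/200)) = 0.041, or about ±8.0 percentage points at 95%. With a 10% rate and RR = 0.5, an imbalance of that size moves an arm's rate by 0.080 × 0.10 × 0.5 = 0.004, or 0.4 points. This is noise in either direction, and small beside the possible effect of pooling.

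**Precision after splitting.** At an assumed 10% rate, the 95% half-width is 1.96 × √(0.1 × 0.9/200) = 4.2 points for 200 De Novo participants, against 1.96 × √(0.1 × 0.9/500) = 2.6 points for all 500. With no events, the 95% upper bound is 1 − 0.05^(1/200) = 1.5%, against 1 − 0.05^(1/500) = 0.6%.

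**The case against.** **The split may exist in redacted text.** Much of Protocol Section 7 and several SAP sections are not visible. In SAP Section 7, the sentence on Safety Population counts breaks off after the words on treatment group, where a subgroup clause could have stood. This objection stands. The point concerns the visible tables only, and the main request falls away if hidden text already meets it.

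**Randomisation protects the comparison.** Completers are randomised to both arms, so the contrast is not confounded. A reader might infer that pooling biases atogepant against SOC within the trial. The documents do not support that: the comparison is valid for the enrolled mix. What remains is whether it carries over to new users.

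**SOC treatment is also fitted to tolerance.** Every participant must be a candidate for an SOC drug, the investigator chooses it with the participant, and it may be changed or stopped during the study. This is true, but the candidacy rule applies to both enrolment categories and the tailoring happens after entry. Neither is selection on having already completed treatment with the drug.

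**The entry filter is narrow.** It removes only AEs thought to signal an unacceptable risk. Completers with ordinary tolerability complaints can enter, so RR may be near 1. This also stands, and it is why no size can be asserted.

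**The amendment log.** SAP Appendix II records: "Remove ISS related subgroup analyses in the summary tables for disposition, exposure, and TEAEs". A reader might infer that a TEAE table by enrolment category was dropped. The entry names no subgroup. Disposition is on the same list, yet the current disposition section still splits by enrolment category. A log also describes superseded text, so nothing here rests on it.

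**Stratified randomisation.** A reader might conclude that allocation should have been stratified by enrolment category. The gain is about 0.4 points under the assumptions above. Amendment 2 (April 2020) allowed remote conduct only from Visit 14 onwards and the SAP was signed in June 2020, so the question is probably moot.

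**Conclusion.** The point holds as a limit on what the pooled tables can show. Up to 60% of the atogepant arm may be Completers. Those previously on atogepant were selected for finishing on it without an AE judged an unacceptable risk, and the visible AE tables do not separate them. Pooled atogepant AE and AE-discontinuation rates may therefore understate those for new users.

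Two stronger statements go too far. One is that the rates are in fact diluted: w, f and RR are all absent from the documents, and the effect is nil if f = 0 or RR = 1. The other is that Completers as a group are known atogepant tolerators: SAP Section 7 shows that they include people who were on placebo, about whom the filter says nothing regarding atogepant.

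The ratio of 0.70 to 0.82 is an upper scenario. It needs the maximum Completer share, every Completer previously on atogepant, and an assumed RR of 0.5 to 0.7. With half of them from placebo it is 0.85 to 0.91.

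The mismatch in the De Novo definition is a wording fault that does not depend on these assumptions. Protocol 4.2 lists Completers as a separate named group, so classification is workable in practice, but the text should not leave it open.

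This is a cheap improvement bearing on the study's only objective. It does not show that the trial's comparison is invalid.

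**What to change.** 1. Unless redacted text already does so, add to SAP 11.1 the overall AE summary, TEAEs, TESAEs and TEAEs leading to discontinuation, each by arm within three groups: De Novo, Completers previously on placebo, and Completers previously on atogepant. Keep the pooled tables alongside.
2. Use one De Novo definition in the Protocol Summary, Protocol 4.2 and SAP Section 4, worded so that a prior-placebo Completer cannot fit both groups or count towards the floor of 200.
3. Optionally, give the between-arm difference stratified by enrolment category (for example, Mantel-Haenszel). The visible safety analyses are descriptive, so this is an extra and not a correction.

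The cost is SAP wording and repeat runs of existing tables on variables that SAP Section 7 already uses. No change in sample size or randomisation is needed. The price is lower precision: about ±4.2 points for 200 De Novo participants at an assumed 10% rate, against ±2.6 for the pooled 500. Smaller Completer subgroups would be less precise still, so the split tables should be read as descriptive.
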